1. BACKGROUND AND RATIONALE

1.1 Pulmonary arterial hypertension (PAH)

PAH is an uncommon condition characterised by pre-capillary resistance to pulmonary blood flow in the absence of airway or parenchymal lung diseases, left heart failure or chronic thromboembolism (1,2). The resultant elevation in pulmonary artery pressure places an increased pressure load on the right ventricle, leading to right heart failure and premature death.

In around 50% of patients there is no identifiable underlying cause, and patients are classified as idiopathic PAH or, where there is a family history, heritable PAH. Histological examination of post-mortem or transplantation PAH lung tissue shows marked pulmonary arterial remodelling with vascular cell proliferation narrowing the vascular lumen (3).

The estimated prevalence of PAH is 15 per million (2,4). It affects people in middle age and is an unmet clinical need. Five-year mortality for idiopathic/heritable PAH managed by experienced centres in the UK is around 58% (5). The current licensed treatments [prostanoids, endothelin receptor antagonists, phosphodiesterase type 5 inhibitors, and soluble guanylate cyclase stimulator] focus on pharmacologically manipulating 3 signaling pathways better known for regulating vascular tone (1,2,4). These treatments have little impact on the underlying vascular remodeling and do not arrest or reverse the course of the condition.

The past few years have seen attempts to target pulmonary vascular remodeling directly with antiproliferative or anti-inflammatory drugs (6). We have shown that pharmacological and gene modulation of the 18kDa Translocator Protein (TSPO) improves endothelial function in primary human endothelial cells treated with PAH-relevant activating stimuli. Furthermore, in rodent models, we have shown that this improvement in endothelial function mediated by TSPO modulation reduces total pulmonary resistance, implying that endothelial dysfunction drives pulmonary vascular resistance. In this study, we wish to test this hypothesis in humans. To do so, we will use the TSPO ligand XBD173 as a tool compound. We have shown that XBD173 reduces activation of endothelial cells in people with multiple sclerosis (MS). Here, we will use it to reduce endothelial cell activation in people with PAH, in order to determine if there are associated changes in total pulmonary resistance (TPR).

1.2 XBD173

XBD173 binds the mitochondrial membrane Translocator Protein (TSPO) with high affinity and was developed in a partnership between Novartis and Dainippon Sumitomo Pharma for the treatment of anxiety. Development was ceased at Phase IIa due to lack of efficacy as an anxiolytic. XBD173 has been used in several studies in healthy volunteers and people with multiple sclerosis and has been well tolerated, with a side effect profile similar to placebo (see more details in Section 4 below).

XBD173 in doses of 1 to 2mg/kg improves endothelial function and reduces total pulmonary resistance and vascular remodelling in two animal models of pulmonary hypertension – the monocrotaline and Sugen-hypoxia rat. Genetic knock-out of TSPO in the rat attenuates the development of hypoxia-induced pulmonary hypertension, consistent with XBD173 acting as an antagonist of TSPO.

2. STUDY OBJECTIVES

Primary objective: To determine whether changes in endothelial cell dysfunction are associated with changes in total pulmonary resistance in patients with pulmonary arterial hypertension

There are no secondary objectives

3. STUDY OUTCOME MEASURES

3.1 Primary measures evaluating effect:

1. Change in plasma sVCAM1, e-selectin, GDF-15 and NT-proBNP by week 8
2. Change in total pulmonary resistance by week 8

3.2 Secondary outcome measures:

There are no secondary outcome measures

3.3 Exploratory outcome measures:

- Change in total pulmonary resistance from baseline according to rs6971 (a genetic variant that regulates XBD173 activity).
- Change in plasma proteome from baseline at 8 weeks.

4. Design

4.1 Overall study design and plan

Patients will be invited to participate by their local pulmonary hypertension hospital. The first 2 participants will be treated with XBD173 90mg once daily for 8 weeks. The first patient will be followed for at least 2 weeks before the second patient starts the XBD173. Subsequent participants will be treated with XBD173 90mg once daily for 2 weeks at intervals of at least 2 week and if the drug is tolerated (defined as an absence of grade 2 adverse events) the dose will be increased to 90mg twice daily for a further 6 weeks. The total period of treatment for each patient is 8 weeks, followed by 4 weeks follow up off XBD173. If a grade 2 AE occurs during 90mg once daily dosing, the participant will be withdrawn. If a patient does not tolerate 90mg twice daily, the local PI will determine whether to stop XBD173, reduce the dose to 90mg once daily or pause dosing and restart at 90mg once daily.

The starting dose of 90mg OD is based on experience from studies of XBD173 in healthy volunteers and in patients with multiple sclerosis.

Rupprecht et al randomised 71 healthy volunteers to 7 days treatment with placebo, 10, 30, or 90 mg/day XBD173 or 2 mg/day alprazolam (PMID: 19541954). The number of side effects reported with XBD173 was comparable to the incidence in the placebo group. In contrast, a much higher incidence was reported by the alprazolam-treated group.

In addition, 4 studies have been sponsored by Imperial College London using XBD173. In all studies XBD173 was well tolerated with no SAEs:

17/LO/0566. This study recruited healthy volunteers (n=31) and people with MS (n=12) and administered XBD173 90mg for 7 days. (To be submitted for publication September 2022).

14/LO/0343. This study recruited people with MS (n=6) and administered a single dose of XBD173 (90mg) prior to PET scanning with 11C-GE180. (PMID: 30796709).

12/LO/0735. This study recruited healthy volunteers (n=6) and administered a single dose of XBD173 ranging from 10mg-90mg prior to PET scanning with 11C-PBR28. (PMID: 24623083).

13/LO/1916. This study recruited healthy volunteers (n=6) and people with MS (n=6) and administered a single doses of XBD173 (90mg) prior to PET scanning with 11C-PBR28. (PMID: 30796709)

The proposed study will recruit patients with PAH attending specialist clinics that have both an approved implanted cardiopulmonary monitor (CardioMEMS™ Heart Failure system) and an activity monitor (a Fitbit activity monitor) that permits remote sensing. The monitors will have been implanted on clinical grounds; specifically, to aid control of pulmonary hypertension by enabling more personalised dose adjustments to licensed treatments. Despite this, the drugs are not curative and patients live with very high pressures (typically 5 times normal resting pressures in a healthy individual). Patients with stable readings for at least a month will be considered for recruitment. These stable readings provide a good baseline from which to measure the effect of the study drug and relate to changes in blood biomarkers.

Remote sensing offers greater oversight of the patient and closer safety monitoring. Remotely acquired patient data are reviewed twice a week via a central clinical team based in Sheffield. Relevant data will be shared as de-identifiable information, and sent to Imperial College London (upon request) as pseudonymised (coded) data if there are any concerns regarding patients' safety. Follow-up would be scheduled by telephone or video conferencing with hospital visits being optional.

The most common side effects reported with XBD173 include nervous system and gastrointestinal symptoms, but the frequencies of these side effects are no higher than placebo.

If a patient is unable to continue with the prescribed dose of XBD173 to 8 weeks, they will be withdrawn from the study.

The end of the study will be the last visit of the last subject.

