4.3.4 Discontinuation criteria

It is possible that the Sponsor, REC or HRA request termination of the study if there are concerns about conduct or safety, or due to a change in the opinion of the Ethics Committee.

When the Sponsor is aware of information on matters concerning the quality, efficacy, and safety of the study drug, as well as other important information that may affect proper conduct of the clinical study, the Sponsor may discontinue the clinical study and send a written notice of the discontinuation along with the reasons to the Investigators. Patients will be informed that they have the right to withdraw from the study at any time for any reason, without prejudice to their medical care. The site Investigator/Chief Investigator can discontinue subjects from the study for any of the following reasons:

1. Occurrence of an unacceptable Adverse Event due to Grade 2 or above defined by the NCI Common Terminology Criteria for Adverse Events (version 5.0, 2017), adapted for this study -see [Appendix 2](#).
2. Subject request
3. Subject is lost to follow-up
4. Administrative reasons
5. Development of an intercurrent illness, condition, or procedural complication, which would interfere with the subject's continued participation
6. Patient becomes pregnant

The site Investigator/Chief Investigator also reserves the right to discontinue subjects in the interest of subject safety and welfare. Investigators must contact all participants and the hospital pharmacy (where applicable) to notify them of the termination of the study. In cases of an early termination (discontinuation), a follow-up telephone assessment will be performed 4 weeks \pm 3 days -see [Appendix 1](#).

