6.4 Hospital assessment (Week 2 ± 3 days)

Patients will attend for safety, urinary pregnancy test (if indicated) and research blood tests, to check concomitant medications, and for the occurrence of AEs. Following completion of these procedures and review of the blood tests, the physician can increase the dose of XBD173 to 90mg twice daily.

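### Section 4.1 sets both the dose-escalation gate and the mandatory once-daily withdrawal rule at grade 2 alone; both should read grade 2 or above

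*Protocol*

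**What the plan says.** Section 4.1 gives the gate for participant 3 onwards after two weeks of once-daily dosing: "if the drug is tolerated (defined as an absence of grade 2 adverse events) the dose will be increased to 90mg twice daily". It gives the withdrawal rule for the lower dose: "If a grade 2 AE occurs during 90mg once daily dosing, the participant will be withdrawn". Both name grade 2 only.

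On the higher dose the section is flexible: "If a patient does not tolerate 90mg twice daily, the local PI will determine whether to stop XBD173", with a reduction to once daily, or a pause and restart at once daily, as the alternatives. It also has a rule without a grade: "If a patient is unable to continue with the prescribed dose of XBD173 to 8 weeks, they will be withdrawn from the study".

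Section 4.3.4 is a general list: "The site Investigator/Chief Investigator can discontinue subjects from the study for any of the following reasons". Its first entry is "Occurrence of an unacceptable Adverse Event due to Grade 2 or above", graded by CTCAE version 5.0 as adapted in Appendix 2, which is a separate file and not shown.

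Section 6.4 has AEs checked and bloods reviewed at Week 2, after which "the physician can increase the dose of XBD173 to 90mg twice daily". It repeats neither the AE criterion nor the limit to participant 3 onwards. That limit does stand in the study summary, in 4.1 and in 5.4. Section 4.1 also says: "The first 2 participants will be treated with XBD173 90mg once daily for 8 weeks". The summary and 5.4 describe escalation without an AE condition.

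**The concern.** A tolerability gate and a stopping rule are normally thresholds: a given grade and anything worse. Section 4.1 names a single grade, so the more severe events fall outside both of its rules. It is also the only place in the protocol that states an AE criterion for escalation, so its wording carries the whole rule. What is at stake is the safety of an individual participant at the step to the higher dose, and whether a serious event on once-daily dosing leads to withdrawal by rule or by judgement.

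**Working it through.** The plan states no figure to reproduce, so the check sets the rules side by side.

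**Step 1. Apply each rule, as worded, to a participant from number 3 onwards during the first two weeks.** The columns are: gate in 4.1, mandatory withdrawal in 4.1, discretionary discontinuation in 4.3.4.

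| Events on once-daily dosing | Gate passed? | Must be withdrawn? | May be discontinued? |
|---|---|---|---|
| None, or grade 1 only | Yes | No | Not on AE grade |
| At least one grade 2 event | No | Yes | Yes, if judged unacceptable |
| Grade 3 or higher only | **Yes** | **No** | Yes, if judged unacceptable |

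The third row is the defect. The worse event gets the more lenient result under both rules in 4.1, and the gate then directs an increase. For participants 1 and 2, who have no escalation step, only the withdrawal column applies, and the same gap appears there.

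**Step 2. Check whether another rule closes the third row.** The rule on being unable to continue the prescribed dose is mandatory, but it turns on inability rather than grade, so it closes the gap only in part. The first entry in 4.3.4 has the right threshold but is permissive. The closing sentence of that list also lets the investigator discontinue for safety and welfare with no grade limit, again at discretion. The conditions in 11.6 stop recruitment; they do not set an individual's dose. None of these supplies the missing words.

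**Step 3. Count the decisions that the gate governs.** Planned participants 6, less the 2 who stay on once daily: 6 − 2 = 4 decisions. The dose reached is 2 × 90 = 180 mg/day. These figures describe the reach of the rule, not the number of decisions the wording would change. That number would be those participants with a grade 3 or higher event and no grade 2 event, for which the protocol gives no rate.

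**Step 4. Test the obvious correction against the rest of 4.1.** Adding *or above* to the withdrawal sentence, with no other change, leaves it applying to any once-daily dosing. A participant stepped down from twice daily because of a grade 2 or higher event that persists on once daily would then have to be withdrawn, which undoes the step-down that 4.1 allows. The rule therefore needs a limit to once-daily dosing as first assigned: all 8 weeks for participants 1 and 2, and the first 2 weeks for participants 3 onwards.

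**The case against.** The best reply is that no sensible investigator would withdraw someone for a grade 2 event and then escalate someone with a grade 3 event. Section 4.3.4 shows what was meant, and the investigator can always stop treatment for safety. That stands as to intent, and it is why the point is minor. It does not make the wording correct: a rule that decides dose should state its threshold, and the safeguards are discretionary.

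Three stronger readings are tempting, and the protocol does not support them.

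- A reader might infer that 4.1 and 4.3.4 contradict each other, since one requires withdrawal and the other permits it. But 4.3.4 is a general list that also covers subject request, loss to follow-up and pregnancy. It confers authority, and a specific rule for once-daily dosing can stand beside it. A cross-reference is enough.
- A reader might infer that 6.4 allows escalation regardless of AEs, or of participants 1 and 2. But the AE check is among the procedures to be completed before the increase, and the limit to participant 3 onwards is given in three other places. Section 6.4 is an incomplete restatement. The summary and 5.4 leave out the same AE condition, so there is no reason to single out 6.4 on that count.
- A reader might size the problem by exposure. Planned once-daily treatment is 2 × 56 + 4 × 14 = 168 of 6 × 56 = 336 participant-days, or 50%. The escalated regimen of 180 mg/day for 6 × 7 = 42 days compares with at most 90 mg/day for 7 days in the studies cited in 4.1. These are context only. The first counts all planned once-daily dosing and the second describes the regimen; neither measures what the wording changes.

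**Conclusion.** The point holds as a minor safety-wording error. Both AE-grade rules in 4.1 omit grades above 2, and on a literal reading a participant with only a grade 3 or higher event on once-daily dosing passes the gate and is not subject to mandatory withdrawal. The intended meaning is almost certainly grade 2 or above. No endpoint, analysis or sample size is affected.

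The practical size cannot be estimated and is probably small, because it needs both such an event and literal application of the rule. The conclusion rests on the wording of 4.1 and 4.3.4 alone. It assumes that an event recorded as grade 3 or higher is not also recorded as grade 2, and that the adapted grading in Appendix 2 does not redefine the thresholds in 4.1.

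**What to change.** In 4.1:

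- Define tolerability as no AE of *grade 2 or above*.
- Make withdrawal mandatory for an AE of *grade 2 or above* during once-daily dosing as first assigned, that is, all 8 weeks for participants 1 and 2 and the first 2 weeks for participants 3 onwards. State that once-daily dosing after a step-down from twice daily stays with the local PI's judgement.

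For consistency:

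- Have 6.4, 5.4 and the study summary refer to the 4.1 criterion, and have 6.4 also say that the increase is for participant 3 onwards.
- Have 4.3.4 refer to the mandatory rule in 4.1 and otherwise remain permissive.

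The cost is a wording amendment, with its usual approval. Visits, assessments, endpoints, analysis and sample size stay as they are.

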4.2 Discussion of study design

This is an open label study. The aim of the study is to use XBD713 as a tool to modulate endothelial cell function, and to determine whether this is associated with a change in total pulmonary resistance (TPR). Patients with implanted devices act as their own control. A change in total pulmonary resistance from a stable baseline can be reasonably attributed to the study drug and would be expected to be accompanied by a reduction in plasma pro-NT-BNP. Patients will continue to be monitored at the end of the study, as part of clinical practice as the devices remain implanted, and any change in total pulmonary resistance return to baseline after discontinuing XBD173 will add weight to the interpretation.

No intervention or procedure which would normally be considered a part of routine care will be withheld.

[figure not shown]

4.3.1 Inclusion criteria

1. Subjects aged between 18-75 years old
2. PAH which is: idiopathic; PAH heritable; PAH associated with connective tissue disease; PAH after \geq 1 year repair of congenital systemic to pulmonary shunt; or PAH associated with anorexigens or other drugs.
3. Resting mean pulmonary artery pressure \geq 25 mmHg, pulmonary capillary wedge pressure \leq 15 mmHg, PVR $>$ 5 wood units, and normal or reduced cardiac output, as measured by a previous right heart catheterisation (RHC).
4. Have an insertable FDA/CE cardiac rhythm monitor and pulmonary artery pressure monitor that captures cardiopulmonary haemodynamics and daily activity.
5. Six-minute walking distance $>$ 50m at entry
6. Stable on an unchanged PAH therapeutic regime comprising at least 2 therapies licensed for PAH (any combination of endothelin receptor antagonist, phosphodiesterase inhibitor or prostacyclin analogue) for at least 1 month prior to screening
7. Subjects willing to be genotyped for genes that influence XBD173 activity
8. Able to provide written informed consent prior to any study mandated procedures
9. Contraception: Women of childbearing potential are eligible to participate after a negative highly sensitive pregnancy test if they are taking a highly effective method of contraception during treatment and until the end of relevant systemic exposure. As the oral contraceptive is an exclusion criterion, the following methods are permitted:
 - sexual abstinence
 - intrauterine device (also called IUD)
 - intrauterine hormone-releasing system (also known as IUS)
 - bilateral tubal occlusion
 - vasectomised partner

*Definition of fertile females (women of childbearing potential) and of fertile men:

For the purpose of this document, a woman is considered of childbearing potential, i.e. fertile, following menarche and until becoming post-menopausal unless permanently sterile. Permanent sterilisation methods include hysterectomy, bilateral salpingectomy and bilateral oophorectomy. A postmenopausal state is defined as no menses for 12 months without an alternative medical cause. A high follicle stimulating hormone (FSH) level in the postmenopausal range may be used to confirm a post-menopausal state in women not using hormonal contraception or hormonal replacement therapy. However in the absence of 12 months of amenorrhea, a single FSH measurement is insufficient. For the purpose of this document, a man is considered fertile after puberty unless permanently sterile by bilateral orchidectomy.

4.3.2 Exclusion criteria:

1. Unable to provide informed consent and/or are non-fluent speakers of the English language
2. Hypersensitivity to XBD173 or to any of the excipients
3. Clinically-significant renal disease (confirmed by creatinine clearance $<$ 30 ml/min per 1.73m²)
4. Clinically-significant liver disease (confirmed by serum transaminases $>$ 2 times than upper normal limit)
5. Anaemia confirmed by haemoglobin concentration $<$ 10 g/dl

- 6. Individuals known to have haemoglobinopathy sickle cell disease, thalassaemia**
- 7. Hospital admission related to PAH or change in PAH therapy within 3 months prior to screening**
- 8. History of left-sided heart disease and/or clinically significant cardiac disease, including but not limited to any of the following:**
 - b. Aortic or mitral valve disease (stenosis or regurgitation)**
defined as greater than mild aortic insufficiency, mild aortic stenosis, mild mitral stenosis, moderate mitral regurgitation
 - b. Mechanical or bioprosthetic cardiac valve**
 - c. Pericardial constriction, effusion with tamponade physiology, or abnormal left atrial size.**
 - d. Restrictive or congestive cardiomyopathy**
 - e. Left ventricular ejection fraction $\leq 50\%$ (measured in echocardiogram at screening)**
 - f. Symptomatic coronary disease**
 - g. Significant (2+ for regurgitation) valvular disease other than tricuspid or pulmonary regurgitation**
 - h. Acutely decompensated left heart failure within 1 month of screening**
 - i. History of untreated obstructive sleep apnoea**
- 9. Evidence of significant lung disease on high-resolution CT (if available) or recent (performed within 12 months) lung function, where $FEV1 < 50\%$ predicted and $FVC < 70\%$ predicted, and DLCO (or TLCO) $< 50\%$ predicted if any CT abnormalities; judged by the Site Physician**
- 10. Patients with a history of uncontrolled systemic hypertension**
- 11. Acute infection (including eye, dental, and skin infections)**
- 12. Chronic inflammatory disease including HIV, and Hepatitis B**
- 13. Women of childbearing potential who are pregnant or breastfeeding (if applicable)**
- 14. Patients who have received an Investigational Medicinal Product (IMP) within 5 half-lives of the last dose of the IMP or 1 month (whichever is greater) before the baseline visit**
- 15. Use of the following medications or therapies:**
 - P450 CY3A4 inhibitors
 - Potent: Boceprevir, Clarithromycin, Cobicistat, Idelalisib, Itraconazole, Ketoconazole, Nelfinavir, Ritonavir, Saquinavir, Telaprevir, Telithromycin, Voriconazole
 - Moderate: Aprepitant, Conivaptan, Crizotinib, Diltiazem, Dronedarone, Erythromycin, Fluconazole, Imatinib, Isavuconazole, Nefazodone, Netupitant, Nilotinib, Posaconazole, Tofisopam, Verapamil
 - Unclassified: Delavirdine
 - P450 CY3A4 inducers
 - Potent: Carbamazepine, Enzalutamide, Fosphenytoin, Mitotane, Phenytoin, Rifampicin
 - Moderate: Bosentan, Efavirenz, St John's wort
 - Unclassified: Barbiturates, Nevirapine, Primidone, Rifabutin, Rifapentine

- oral contraceptives
- oral anticoagulants or antiplatelet agents other than low dose aspirin
- levothyroxine

